## **Statistical Data Analysis Plan extracted from IND dated 09/28/2020**

The difference between the 2 groups in total VAS score from the cue reactivity testing at visit 3 will be assessed with a linear mixed model. The model will include all relevant clinical parameters e.g., miricorilant plasma concentration. Naturalistic secondary outcome measures i.e., number of standard drinks per day collected with the Timeline Followback (TLFB) will be analyzed for group differences with the same strategy as the primary endpoint. Safety will be primarily assessed by means of adverse events (AEs). Additional clinical evaluations for safety assessments will include routine monitoring of blood chemistry, hematology, urinalysis, vital signs, and ECG. Safety analysis will be based on all patients included in the study population and presented by treatment arm.

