25.0 Blood Draw Details

25.1 *Source of Blood Samples (Check all that apply.)

Subjects as part of a clinical trial
 Blood Donors with a condition or a disease that are NOT part of a clinical trial
 The Scripps Research Institute (TSRI) Normal Blood Donor Service (NBDS)
 OTHER normal blood donors NOT part of the Normal Blood Donor Service (NBDS)

If Other, please explain where the samples are coming from:

(If you are using TSRI NBDS, be sure to include an NBDS Donor Information Form with your submission.)

25.2 *Describe in simple language how this blood will be used.

Blood samples will be used for serum pregnancy test (if female), complete metabolic panel (CMP), that includes gamma glutamyl transferase (GGT), and complete blood count (CBC w/diff) for general bodily functioning. In addition, blood will be drawn for drug concentration and to measure plasma cortisol, aldosterone, and selected cytokines.

25.3 *How frequently will the blood samples be collected?

Less Than 2 Times per Week
 More Than 2 Times per Week
 N/A Outside Scripps

25.4 *How much blood (ml) will be collected each draw?

Less Than 50 Mls (10 teaspoons)
 More Than 50 Mls (10 teaspoons)
 N/A Outside Scripps

25.5 *Who will draw the blood?

[name], our Research Medical Assistant who is a certified phlebotomist, will draw the blood samples.

25.6 If blood will be obtained outside of Scripps, will the samples be obtained with Informed Consent? (Note: If Yes, attach a copy of the IRB approval and/or approved Informed Consent from the other site to the Initial Review Submission Form.)

Yes
 No
 N/A

If No, please explain why:

25.7 *Will the blood be used for genetic analysis?

Yes No

25.8 If Yes, will the results of the genetic analysis be shared with subjects? (REMINDER: If you plan to share the results, consider adding the Genetic Information Nondiscrimination Act language to the consent. Please click on the grey 'Help' button in the upper right to view the genetic language template.)

Yes No

If Yes, explain how the results will be used:

25.9 *Will ALL blood samples used in the study be de-identified?

Yes No

25.10 *Will leftover de-identified blood be used for other studies? (Future plans must first be reviewed by a Scripps IRB.)

Yes No

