28.0 Study Plan - Details

28.1 Research Methods - Include the Schedule of Events or provide a precise description of the data collection methods. (Attach the Schedule of Events to the Initial Review Submission Form, if applicable)

This is a randomly assigned, double-blind, placebo-controlled outpatient study of the effectiveness of 2-weeks of oral CORT118335 (900 mg/d) for decreasing alcohol cue-induced craving for alcohol in subjects with alcohol use disorder of moderate or greater severity (AUD-MS). Alcohol cue reactivity procedures will be conducted on the last day of dosing (Day 14), with endpoints selected to assess the effects of drug on alcohol cue-induced craving in the lab, as well as on naturalistic measures of protracted abstinence involving sleep, mood, craving and relapse to drinking. A positive signal on such indices would lend support to the potential utility of the drug for the treatment of alcohol use disorder.

Initial Phone Screening

Clinically trained study personnel provide information about the study. Interested individuals who meet initial eligibility criteria are scheduled for a face-to-face intake evaluation.

Visit 1, Screening

After providing written informed consent, subjects complete a Screening Visit for evaluation of eligibility (see Table 1). The Mini-International Neuropsychiatric Interview (MINI; Sheehan & Lecrubier, 2015) for DSM-5 will be administered to determine the inclusion criteria of current AUD with ≥ 4 symptoms and to rule out major psychiatric disorders that would warrant study exclusion. The subject's demographic information, medical and alcohol use history, adverse events and use of concomitant treatments will be recorded using standardized forms. Vital signs and BAC will be assessed, and specimens for urinalysis, serum pregnancy test (if female), urine drug screen, blood chemistry that includes liver function tests (LFTs) and GGT, and complete blood count with differential (CBC w/diff) will be collected by the medical assistant and prepared for same day pick up by LabCorp for analyses. A mini-cue session familiarizes subjects with the cue reactivity lab setting and identifies non- cue-reactive subjects for study exclusion (Visual Analogue Scale [VAS] craving severity rating of alcohol cue ≥ 3 points higher than water cue).

Visit 2, Randomization

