Subjects complete the evaluation for eligibility, including ECG, repeat negative pregnancy test and physical exam. Medically cleared subjects complete baseline clinical assessments and are randomized to receive a 2-week supply of double-blind study medication.

Visit 3, Alcohol Cue Session

Subjects return 2 weeks after randomization to complete the alcohol cue session. The alcohol cue session will last for two hours (Table 2).

Table 2. Alcohol Cue Session Procedures

Baseline

1:00 pm: Subject arrives: BAC, vital signs; adverse events and concurrent drug therapy; urine Elg/Ets screen for alcohol and uds for illicit drug use; blood samples obtained; TLFB; CIWA; clinical assessments (i.e., ACQ, PSQI, BDI, STAI).

1:40 pm: Subject prepped for cue session: electrodes attached, and impedance checked; baseline VAS obtained. Subject given instructions and cue-reactivity practice trial.

Cue-Reactivity Trials

2:00 pm: Step 1- Mood induction: subject exposed to block of 12 affective images (pleasant, unpleasant or neutral), psychophysiological recording.

Step 2- In vivo beverage cue: alcohol or water in front of subject for 90 s while recalling picture-induced mood, psychophysiological recording.

Step 3- Ratings: subjects complete VAS craving, and manipulation check in presence of beverage cue.

Step 4- Beverage removed from testing area after completion of ratings.

2:15 pm: Repeat Steps 1-4 for remaining affect-beverage trial combinations (six trials total).

End of Lab Study Procedures

2:45 pm: Debriefing and relaxation period, subject completes ACQ, and BDI-II to verify return to baseline.

Visit 4, Follow-up

Subjects will participate in a scheduled virtual visit 2-weeks after the cue session and discontinuation of study drug to assess persistence of treatment effects and resolution of any adverse reactions. Motivational interviewing and potential treatment options are provided by a study clinician. The study physician conducts a virtual review with all subjects of Week 3 lab results, ECG, status of any adverse events, and at-home Week 4 pregnancy test results with female subjects.

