The primary hypothesis under test is that treatment with CORT118335, a GR/MR antagonist that modulates the activity of cortisol and aldosterone, will result in significant improvements in subjective craving following alcohol-cue exposure in the lab and in naturalistic measures of protracted abstinence that include relapse to drinking, craving and disturbances in sleep and mood. Support for this hypothesis is provided by pre-clinical and clinical studies of GR and MR antagonists in AUD. Preclinical studies of the GR antagonist, mifepristone, showed reduced alcohol intake in alcohol-dependent rats, but not in non dependent animals, and a double-blind study of 56 non treatment-seeking alcohol dependent subjects showed 1-week of treatment with mifepristone 600mg/d significantly reduced alcohol craving and consumption compared to placebo in the above human lab model (Vendruscolo et al., 2015). We recently completed a randomized, double-blind trial of 1-week of mifepristone 1200 mg/d, 600 mg/d or matched placebo followed by 8-weeks of counseling in 103 treatment-seeking outpatients with AUD. Preliminary analyses replicated the earlier effects of mifepristone found in the lab model involving non treatment seekers with AUD, i.e., significantly decreased drinking for the week on drug and for the following 2 weeks in individuals who did not have abstinence as a treatment goal. Effectiveness in this group was linearly related to mifepristone plasma level, with equivalent efficacy in men and women. Consistent with the half-life of the drug, effects were not detected after 2 weeks post treatment. Individuals who entered treatment with abstinence as a treatment goal did well with counseling, regardless of whether their assigned drug was mifepristone or placebo. Mifepristone significantly ($p < 0.05$) improved ALT and GGT relative to placebo. Taken together, the preclinical, human lab model and clinical trial results lend support to the therapeutic potential of GR antagonism as a treatment strategy for AUD.

¹A relationship between the aldosterone-MR pathway and alcohol drinking also has been found in studies across 3 species: rats, monkeys and humans (Aoun et al., 2018). Of note, non-abstinent AUD patients had significantly higher circulating aldosterone levels than abstinent AUD patients, and aldosterone levels were positively correlated with the quantity of alcohol consumed, as well as with craving and anxiety scores.

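### The primary model adjusts the drug–placebo comparison for miricorilant plasma concentration, a consequence of treatment that is zero on placebo, so the group coefficient no longer estimates the treatment effect

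*SAP*

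**What the plan says.** The SAP is a single paragraph taken from the IND. It defines the primary analysis as follows: "The difference between the 2 groups in total VAS score from the cue reactivity testing at visit 3 will be assessed with a linear mixed" (cut short of its final word). The next sentence reads "The model will include all relevant clinical parameters e.g., miricorilant plasma concentration". In context, the model meant is the two-group model just introduced, and concentration is the only covariate the SAP names. The number of standard drinks per day from the Timeline Followback (TLFB) "will be analyzed for group differences with the same strategy as the primary endpoint".

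The comparator is placebo (Protocol, section 28.1). Section 25.2 states that "blood will be drawn for drug concentration and to measure plasma cortisol, aldosterone, and selected cytokines". It gives no time for the concentration sample, but the sample must follow dosing to be informative, and the Visit 3 schedule (section 28.1, Table 2) includes a blood draw before the cue trials.

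Section 29.1 describes the group's preliminary results with a related drug, mifepristone, in outpatients who did not have abstinence as a goal: "Effectiveness in this group was linearly related to mifepristone plasma level, with equivalent efficacy in men and women".

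Neither document confines the concentration term to a separate analysis or to the active arm. Neither says how it is to be centred, or which contrast or test carries the primary conclusion.

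**The concern.** A covariate in a randomised comparison should be fixed before randomisation. Miricorilant concentration is produced by the assignment. It is zero for everyone on placebo and positive for those who take the drug, so it is strongly correlated with arm. It may also be the route by which the drug acts.

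Adjusting for it has two consequences. To the extent that the effect rises with concentration, the concentration term takes that part of the effect away from the group term. To the extent that it does not, the overlap between the two terms inflates the standard error of the group coefficient. Either way, a drug that works can show no significant group effect in a proof-of-concept trial of 50 subjects. The mixed model gives no protection, because arm and concentration both vary only between subjects.

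**Working it through.** **Inputs from the documents.** Two arms, placebo control; 50 subjects in total (Protocol, section 37); total VAS at Visit 3 as the primary outcome; concentration in the model (SAP). Section 37.8 justifies 50 by screening yield alone, so there is no power calculation to reproduce.

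**Assumptions, because the documents give no values.** 1:1 allocation (n = 25 per arm), two-sided alpha 0.05, true effect −0.8 SD (lower craving on drug), residual SD 1, lognormal concentration in the active arm with coefficient of variation (CV) 0.3, 0.5 or 0.8, and concentration 0 on placebo. Ordinary least squares on one value per subject is used.

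**Step 1: what the group coefficient becomes.** Fit y = a + b·group + k·conc. Placebo subjects all have conc = 0, so they fix a at the placebo mean. The active arm alone fixes the slope k and the intercept a + b. Hence

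b = (active-arm regression line extrapolated to zero concentration) − (placebo mean).

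If the effect is −0.8 × conc, with mean concentration scaled to 1, the active-arm line meets the placebo mean at zero concentration and b = 0.

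**Step 2: its variance.** Without concentration, Var(b) = σ²·2/n. With it, Var(b) = σ²·[2/n + 1/((n−1)·CV²)]. The ratio is 1 + n/(2(n−1)·CV²) = 1 + 0.521/CV² for n = 25:

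| CV | Variance ratio | SE ratio |
|---|---|---|
| 0.3 | 1 + 0.521/0.09 = 6.79 | 2.61 |
| 0.5 | 1 + 0.521/0.25 = 3.08 | 1.76 |
| 0.8 | 1 + 0.521/0.64 = 1.81 | 1.35 |

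**Step 3: simulation** (4,000 trials per row). Without concentration, the normal approximation gives 80.7% power for 0.8 SD and 25 per arm.

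| CV | How the effect depends on concentration | Group only: estimate, power | Group + concentration: estimate, SE, power |
|---|---|---|---|
| 0.3 | Fully linear | −0.81, 79% | −0.01, 0.76, 5% |
| 0.3 | Half linear | −0.79, 77% | −0.38, 0.76, 8% |
| 0.3 | None (flat) | −0.80, 80% | −0.81, 0.76, 19% |
| 0.5 | Fully linear | −0.80, 76% | 0.00, 0.52, 4% |
| 0.5 | Half linear | −0.80, 79% | −0.40, 0.52, 12% |
| 0.5 | None (flat) | −0.80, 79% | −0.80, 0.52, 33% |
| 0.8 | Fully linear | −0.80, 72% | 0.00, 0.40, 5% |
| 0.8 | Half linear | −0.80, 78% | −0.40, 0.41, 17% |
| 0.8 | None (flat) | −0.80, 80% | −0.80, 0.40, 50% |

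The simulated SEs are slightly above the formula because the sample CV varies between trials.

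**Step 4: is the information lost?** No. The active-arm line passes through the active-arm means, so b + k × (mean active concentration) equals the plain difference in means exactly. Centring concentration within the active arm, with placebo set to 0, returns that difference as the group coefficient. For the fully linear case this gave −0.80 to −0.81 with 78–80% power. The loss comes from reading the uncentred group coefficient as the treatment effect.

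**The case against.** The strongest reply is that the SAP wording is loose rather than wrong. It is a short extract, it introduces concentration only as an example, and the authors may have meant a separate exposure–response analysis. The harm also requires that concentration enters uncentred and that the conclusion rests on the single group coefficient. Centring within the active arm avoids it, and a joint two-degree-of-freedom test of group and concentration would largely avoid the loss of power (about 69–88% under the same assumptions at CV 0.3 to 0.7). Those points are correct, and they make it too strong to say that the fitted model contains no answer to the trial's question. They do not rescue the text: the SAP specifies none of these devices, and an analyst who follows it with default software would report the wrong coefficient. Leaving the matter open also allows the choice to be made after unblinding, when it could move the estimate from the full effect to none.

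The evidence that the effect runs through concentration is also limited. It comes from preliminary analyses of a different drug, on drinking rather than cue-induced craving, in treatment-seeking outpatients and only those without an abstinence goal. The fully linear case is therefore plausible but not established for miricorilant. The flat case needs no such evidence, and it still costs much of the power.

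Finally, at the higher CVs concentration is far from a duplicate of arm (variance ratio 1.81 at CV 0.8), so the size of the problem depends on a variability that the documents do not report.

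**Conclusion.** The concern holds. As written, the primary model conditions on a post-randomisation consequence of treatment, and its group coefficient is not the two-group difference the SAP sets out to assess. The TLFB analysis has the same fault.

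Under the stated assumptions, power falls from 72–80% to about 5% if the effect is linear in concentration, to 8–17% if half of it is, and to 19–50% if none of it is. The estimate is biased to about zero in the first case, roughly halved in the second, and unbiased but imprecise in the third. The sizes depend on the assumed effect, CV, allocation and alpha; the direction does not. Zero concentration on placebo is inferred from the design and not stated in the documents. Because this affects the primary analysis, it must be corrected before the data are unblinded.

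**What to change.** In the SAP, delete the concentration example and the open-ended reference to relevant clinical parameters. State that the primary VAS model and the TLFB model contain randomised arm and named pre-randomisation covariates only. The alcohol-minus-water VAS difference from the Visit 1 mini-cue session is a natural candidate for the VAS model, and pre-randomisation drinking for the TLFB model. State also that no on-treatment measure enters these models. That covers drug concentration and also on-treatment cortisol, aldosterone, cytokines and pill counts, which the present wording could admit.

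Add a separate, supportive exposure–response analysis of concentration within the miricorilant arm, labelled as non-randomised, with the sampling time stated.

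The cost is SAP wording only: no new subjects, visits or assays, and the concentration data are still used. Date the change before the blind is broken. If that has already happened, report the comparison without concentration as the treatment effect and say when the decision was made.

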37.10 Inclusion Criteria

*Use the link below to add inclusion criteria.

Order Number	Criteria
1	
 • Male or female volunteers, 18-75 years of age. • Meets DSM-5 criteria for current alcohol use disorder of moderate or greater severity (AUD-MS, ≥ 4 symptoms). • In the month prior to screening, reports drinking ≥ 21 standard drinks per week if male, ≥ 14 if female, with at least one heavy drinking day (≥ 5 drinks/d if male, ≥ 4 drinks/d if female) per week. • Subjects will be non treatment-seekers because the study is not a treatment trial, and to avoid exposing treatment-seekers to alcohol cues. • Subjects must be abstinent a minimum of 3 days (but not more than 7 days) prior to the alcohol cue reactivity lab session. • Negative BAC and EtG/EtS and a CIWA score of ≤ 9 at the time of the lab session. • In acceptable health in the judgment of the study physician, on the basis of interview, medical history, physical exam, ECG, routine urine and blood chemistry. • Females with childbearing potential must have a negative pregnancy test on the screening and randomization visits. • All subjects must agree to use double barrier contraception for the duration of the study and one month thereafter, i.e., males must use condoms and females must use spermicide and/or a non hormonal barrier method, and their opposite sex partner must likewise use an effective non hormonal form of contraception. • Able to provide informed consent and understand questionnaires and study procedures in English. • Willing to comply with the provisions of the protocol and take oral medication.

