37.11 Exclusion Criteria

*Use the link below to add exclusion criteria.

Order Number	Criteria
--------------	----------

1

- Medical conditions that could be aggravated by glucocorticoid and/or mineralocorticoid antagonism, such as: autoimmune disease, hypotension, or postural hypotension.
- Clinically significant findings on physical exam, ECG, urine or blood tests that may increase risk, e.g., serum potassium outside of the normal range.
- Meets DSM-5 criteria for a current major psychiatric disorder, including mood, anxiety or substance use disorders, other than alcohol, nicotine, or mild cannabis use disorders. However, subjects with a history of depression, who have been on a stable dose of anti-depressant medication for at least 3 months, and do not meet DSM-5 criteria for current depression or anxiety disorders may be admitted.
- Has an ACQ total score of ≤ 30 and/or is non cue reactive., i.e., VAS craving severity score < 3 points higher to alcohol cues than to water cues, at Visit 1 (screening).
- Cannot provide a urine drug screen negative for substances of abuse other than alcohol or cannabis.
- Liver function tests more than 3 times the upper limit of normal or elevated bilirubin.
- Pregnant or lactating.
- Treatment within the month prior to screening with (1) an investigational drug, (2) drugs which may negatively interact with study medications, or (3) drugs that may influence study outcomes (e.g., disulfiram [Antabuse], naltrexone [ReVia], acamprosate [Campral], or anticonvulsants.
- Chronic systemic steroid use
- Using drugs that are strong inhibitors and inducers of CYP2C9.
- No fixed domicile and/or no availability by home or mobile telephone.

37.12 Provide justification for inclusion or exclusion of any group (gender, race, ethnicity or other):

All gender, race and ethnicity groups will be included.
Excluded groups include children and pregnant or breast-feeding women.

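### The primary Visit 3 VAS model names no pre-randomisation covariate, although Visit 1 cue ratings already exist for every eligible subject

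*SAP*

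**What the plan says.** The SAP extract defines the primary comparison as "The difference between the 2 groups in total VAS score from the cue reactivity testing at visit 3", assessed with a linear mixed model. On covariates it adds one sentence: "The model will include all relevant clinical parameters e.g., miricorilant plasma concentration". Drinks per day, the named secondary outcome, follows the same strategy. The protocol gives no analysis model that would fill the gap.

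The protocol does collect a relevant rating before treatment:

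- Section 28.1, Visit 1: "A mini-cue session familiarizes subjects with the cue reactivity lab setting" and is also used to identify subjects who do not react to cues.
- Section 37.11 excludes a subject whose VAS craving rating is less than 3 "points higher to alcohol cues than to water cues, at Visit 1 (screening". The rule cannot be applied without both ratings.
- Section 28.1, Visit 2: "Medically cleared subjects complete baseline clinical assessments and are randomized". Randomisation therefore comes after the Visit 1 ratings.
- Section 28.1, Table 2 (Visit 3, last day of dosing): "baseline VAS obtained" before the cue trials, then "Repeat Steps 1-4 for remaining affect-beverage trial combinations (six trials total", crossing three mood conditions with alcohol or water.

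**The concern.** A VAS craving rating to the same type of cue as the endpoint exists for every properly enrolled subject before randomisation, and the extract does not say whether it is used. The only covariate it does name is a drug level, which exists only after dosing.

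Two things are at stake. The first is precision: the trial has 50 subjects, and section 37.8 of the protocol justifies that number by screening yield alone, so no stated power margin makes precision dispensable. The second is a fixed analysis. An open-ended list admits the Visit 1 VAS, the Visit 1 ACQ, the Visit 2 assessments, and even the VAS taken at the start of Visit 3. That last one is labelled a baseline but follows two weeks of dosing, so adjusting for it could remove part of a drug effect.

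Bias is not at stake. An unadjusted comparison of randomised arms is valid.

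**Working it through.** **Inputs.** Total N = 50 (Protocol 37.1, 37.5). The documents give no alpha, power, effect size, SD or allocation ratio, so there is no stated power figure to reproduce. Assumed: 25 per arm with complete data, two-sided 5%, 80% power, and a correlation rho between the Visit 1 rating and the Visit 3 score.

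**One score per subject, unadjusted.** With the noncentral t on 48 df the required noncentrality is about 2.86, so the detectable effect is 2.86 × √(2/25) = 2.86 × 0.283 = 0.81 SD. The normal approximation gives (1.960 + 0.842) × 0.283 = 0.79.

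**One score per subject, adjusted.** One covariate multiplies the variance by (1 − rho²) × (1 + 1/46); the second term is the average cost of estimating its slope. Equivalent unadjusted N = 50 / [(1 − rho²) × 47/46]. At rho 0.3 this is 50 / (0.91 × 1.0217) = 53.8.

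| rho | Detectable effect (SD) | Equivalent N | Power at 0.6 SD |
|---|---|---|---|
| unadjusted | 0.809 | 50 | 54.7% |
| 0.1 | 0.814 | 49.4 | – |
| 0.2 | 0.801 | 51.0 | 55.5% |
| 0.3 | 0.780 | 53.8 | 57.7% |
| 0.4 | 0.750 | 58.3 | 61.1% |
| 0.5 | 0.708 | 65.2 | 66.0% |

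At rho 0 the equivalent N is 48.9. Break-even is at rho = √(1 − 46/47) = 0.146.

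**Effect of the entry cut.** Eligibility truncates the Visit 1 alcohol-minus-water difference, which lowers rho among enrolled subjects. Assume normal ratings with equal variances, alcohol–water correlation r, and a fraction p passing the cut. The variance of the difference falls by a fraction k, and that of the alcohol rating becomes v = 1 − k(1 − r)/2. Then rho′ = rho√v / √(1 − rho²(1 − v)).

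Example: p = 50% and r = 0 give k = 0.637 and v = 0.682, so rho 0.3 becomes 0.251. For p of 50% to 90% and r of 0 to 0.7:

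| Unselected rho | Alcohol-cue covariate, one score: equivalent N | Visit 1 difference as covariate, drug-by-cue contrast: equivalent N |
|---|---|---|
| 0.2 | 50.3 to 50.9 | 49.7 to 50.4 |
| 0.3 | 52.2 to 53.6 | 50.7 to 52.4 |
| 0.5 | 60.1 to 64.5 | 54.9 to 60.6 |

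At rho 0.1 every setting loses a little (49.1 to 49.4). The right-hand column is lower because the cut falls directly on that covariate (v = 1 − k). The separate ACQ cut in 37.11 is not modelled.

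**Trial-level model.** If treatment is tested as drug-by-cue, a covariate that is constant within subject cancels from the alcohol-minus-water contrast and gains nothing. In one simulated data set (50 subjects, two cues by three moods, rho 0.5, alcohol–water correlation 0.5, random intercept and cue slope), the drug-by-cue SE was 0.279 with zero, one or two such covariates. It was 0.253 with a cue-matched covariate and 0.257 with both ratings crossed with cue. Over 8,000 simulated trials per setting without the entry cut, at rho 0.3 to 0.5, the cue-matched covariate was worth 54 to 66 subjects. The alcohol rating alone crossed with cue was worth 50 to 56.

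**The covariate the plan does name.** With placebo concentrations at zero and an assumed coefficient of variation of 30%, 50% or 80% among treated subjects, adding plasma concentration multiplies the variance of the treatment coefficient by about 7.5, 3.5 or 2.1.

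**The case against.** This is an optimisation rather than an error: the plan's wording does not exclude a baseline rating, and the text is an extract from a longer document. Both points are fair. They limit the point to the supplied extract and to advisory weight. An open list still does not prespecify a covariate.

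The gain rests on an assumed correlation. At 0.2, after the entry cut, it is close to nil for a single score and break-even or a small loss for the drug-by-cue contrast. That is correct, and the table shows it. The correlation between the two alcohol-minus-water differences is also a separate quantity from the single-score correlation and may well be lower, so the drug-by-cue figures are the less certain.

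The Visit 1 session is an abbreviated one, whereas Visit 3 has six trials with mood induction, and the total VAS score is not defined. If it pools alcohol and water trials, the alcohol rating is a less exact match. The visit schedule cited in section 28.1 is not in the supplied text, so a better Visit 2 measure cannot be ruled out. These points affect which covariate to name, not whether to name one.

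The SE comparison comes from one simulated data set. It illustrates that a subject-level covariate has no effect on the contrast; the sizes should be read from the repeated simulations.

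Plasma concentration in the primary model is arguably the more serious matter. That is so, and limiting covariates to pre-randomisation variables deals with both.

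The screening parenthesis in section 28.1 and the exclusion in 37.11 word the 3-point threshold differently and should be reconciled. Either reading requires both Visit 1 ratings.

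**Conclusion.** The point holds, as an advisory one. The supplied extract names no pre-randomisation covariate for the primary comparison, and a suitable rating is already collected. The loss is one of precision and of a fixed covariate choice. If rho is 0.3 to 0.5 before the entry cut, adjustment after the cut is worth about 52 to 65 subjects instead of 50 for a single total score, and about 51 to 61 for a drug-by-cue test with a cue-matched covariate. If rho is about 0.2 the gain is negligible, and near zero about 2% of effective sample size is lost. All of this assumes 25 per arm with complete data and normal ratings.

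**What to change.** State in the SAP that covariates in the primary model are pre-randomisation only. This excludes both plasma concentration and the VAS taken at the start of Visit 3. Then name the covariate, according to how the endpoint is analysed:

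- **One total score per subject:** the Visit 1 alcohol-cue VAS as a fixed covariate. It is preferred to the Visit 1 ACQ because it is the same type of rating to the same type of cue.
- **Trial-level data with a drug-by-cue test:** the cue-matched Visit 1 VAS (alcohol rating on alcohol trials, water rating on water trials), or both Visit 1 ratings each with a by-cue term.

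For drinks per day, adjust for the drinking level recorded for eligibility in section 37.10 ("In the month prior to screening, reports drinking"), or for a pre-randomisation TLFB if one is collected.

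The cost is a line of SAP wording once the total score is defined, and no new data. The single or cue-matched covariate uses one model degree of freedom; crossing both ratings with cue uses more. The worst case is about 49 effective subjects instead of 50.
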